7. DATA

7.1 Data Collection

The precise data to be collected and their sources for the study are given as per the below Clinical Research Forms (CRF) and datasets:

CRF 1	Clinical data
Source for Clinical data: Patient’s medical records, including observations and medical/nursing notes, discharge summary and admission form. Includes EDIS export to locate the relevant patients to obtain data from.	
CRF 2	Health Economy data (specifically aimed at out-of-pocket costs for families and measures of quality of life)
Source for Health Economy data: Use of the GenPrem instrument will be for the parent as proxy for the child and as the parent for their own experience with their child’s admission to hospital.	
CRF 3	Implementation Science data (specifically aimed at knowledge, skill retention and fidelity)
Source for Implementation Science data: The Normalisation Process Theory tool will be used and adapted for the staff survey. This survey will be in paper and electronic format depending on what is most suitable for the local team.	

Other Datasets & Collection includes:

Health Economy data (specifically aimed at health care and transportation costs) – sourced as per current Qld Health per day admission costings for the ward and/or Intensive Care and transfer/retrieval costs.

Health Economy data (specifically aimed at implementation costs which includes education costs) – sourced by capturing all education records and monitoring/capturing data on the movement of the transient staff in these regions.

Data will be collected in an online REDCap database. In each site the emergency admissions will be screened for children 0-4 years of age presenting with respiratory symptoms. Data on the baseline demographics, physiology at presentation and initial medical management will be captured. Length of hospital stay, length of oxygen therapy, type of oxygen therapy, and amount of oxygen resources will be captured. Further information will be captured on methods of oxygen therapy. Adverse events will be recorded. For children who required transfer to high level of care, vital signs and clinical diagnosis and medical therapy provided at time of decision to transfer will be collected. Data on respiratory support during transfer, mode and length of transport and data on treatment in accepting hospital and length of hospital stay will be collected. Adherence to the respiratory care bundle will be measured by the number of frequency of deviations from the protocol.

Twelve parents per hospital using a face-to-face structured interview will complete a paediatric proxy health related quality of life measurer (PedsQL).

Historical Control. Admissions (HBCIS) to the participating hospitals in year 2016-2022 will be screened using the same screening log as in the main protocol (Year 2020-2022 will be separately analysed due to impact of COVID-19 pandemic) and the same data collection as above used.

Time Points for Data Collection. All physiological (heart and respiratory rate, temperature) and blood parameters (arterial gases) that are captured in the medical records during the hospital admission and where relevant during the transfer for higher level of care. If admitted to a tertiary hospital, data on respiratory support provided will be captured.

Specific data

The specific data set mirrors in its basic form the data captured in our previous 3 large RCT's using nasal high-flow in children with ARF or bronchiolitis. Additional data on out-of-pocket expenses and lost income will be recorded.

Background data:

Background data collection will be collected as per the CRF. Below outlines some of the specifics which continue the same data collection of the 3 large RCT's.

Demographics:

- Age (on admission)
- Gender
- Weight (on admission)
- Ethnicity
- Diagnosis at admission
- History and risk factors
 - Prematurity (<37 weeks at birth)
 - Previous neonatal respiratory support post delivery
 - Previous Intensive Care admission post delivery
 - Previous hospital admission for respiratory support postnatal period
 - Complex patient
 - Previous Intensive Care admission postnatal period
 - History of chronic lung disease
 - History of congenital lung disease
 - Family history of allergies, asthma, wheeze

7.2 Implementation Science Data and Health economy Data

Several methods including interviews and questionnaires will occur across the study period to capture relevant data on the consumer/s (parents/guardians/carers), health practitioners and health care leaders experience.

Clinical Staff Interviews:

Knowledge and skill retention: Structured face-to-face interviews/questionnaires with local clinical staff to measure knowledge retention prior to implementation and six months post implementation for 12 months. Adherence audit of the respiratory care bundle will be measured comparing actual practice against recommended practice [26] on a 6 monthly interval during the 31 month implementation phase.

The following 5-6 key knowledge domains will be measured:

- Recognition of bronchiolitis or ARF and use of existing guidelines/source of truth
- Oxygen therapy thresholds
- Indication for high-flow
- Indication for escalation of care
- Correct use of high-flow
- Weaning of high-flow

Interviews with open ended questions: Perform structured interviews with selected consumers/parents and clinicians working in the participating hospitals to obtain information regarding socio-economic factors and experience during the study. There will be specific and open ended questions to capture the full image of concerns raised by the local stake holders. A post hoc categorisation will occur.

Hospital System interviews: Standardised interviews with leadership roles to measure adaptation of EBP in the local hospital context, including staff turnover management.

Parent interviews:

A structured interview with 12 parents per hospital in the Control Phase and 12 parents in the Implementation phase will be conducted after obtaining written formal consent (**Figure 3**). The following key domains will be covered:

- Previous experience with hospital admission or transfer
- Socioeconomic data
- Living conditions
- Work interruption, income interruption
- Out of pocket costs, accommodation, transfers

Economic evaluation of the implementation process will be conducted with the aim to evaluate the association between cost of implementation, depth of implementation and how this affects the key primary outcome. An alongside trial cost analysis will be carried out, with the effect of implementation depth and cost regressed against the key primary outcome (adjusting for covariates).

8. STATISTICAL METHOD

8.1. Sample Size

Pre COVID-19, the participating 14 hospitals in Far North QLD have admitted over 4 years (2016-2019) a total of 2532 children with ARF. The transfer rate in these hospitals was during this period 25%. With the implemented intervention of the full study in 14 hospitals, we aim to achieve a reduction in transfers from 25% under the existing respiratory care pathways to 12.5% under the intervention condition (for all children with ARF aged 0-4 years). Our sample size of minimal eligible participants of 90 patients per hospital (1,260 patients in total) achieves over 85% power to detect this difference in transfer rates assuming an intracluster correlation coefficient of 0.1 and using a two-sided test at the 5% level of significance with the Stata function “stepped wedge”. [15, 16] Our calculation under a stepped wedge design assumes a sequential rollout schedule of the intervention that has 4 steps, with 3 or 4 hospitals randomised at each step and an average of 18 patients per hospital per time point within a 6-month interval (i.e. a total of 90 patients per hospital including baseline recruitment). The total trial duration will be 31 months including a 1-month transition period for each hospital.

8.2 Data Analysis

Generalised linear mixed models (GLMMs) will be used to account for cluster hospital effects with adjustment for the rollout time of the intervention and potential district effect and estimate the change in the proportions of PICU transfers (using a logistic link function) as well as the length of stay in acute care settings (using Poisson or negative binomial distributions) under the intervention condition, compared with those under the control condition. Model fit and assumption testing will

be conducted as appropriate within the GLMM framework and significance will be set at $p < 0.05$. The GLMM can handle missing data in the outcome variable under the ignorable mechanism (such as missing completely at random).

8.3 Methods for health economics evaluation

Economic evaluation of the intervention will be conducted using standard approaches and will be from a health care provider and societal perspective. An alongside trial economic evaluation will be undertaken, with primary outcomes of cost benefit/net benefit analysis and cost effectiveness analysis (formulated as the incremental cost-effectiveness ratio [ICER]) in the form of the incremental cost per air transport avoided.

The ICER is the ratio between the incremental cost and the incremental outcome. Incremental cost is the cost difference between the intervention and usual care. Incremental outcome is the outcome difference between the intervention and usual care. The economic evaluation will compare any incremental costs of the intervention (costs accrued in the intervention arm compared to those in the control arm) to the full list of incremental primary and secondary outcome endpoints, all expressed in their natural units of measurement. Given the pilot data and reductions in cost associated with it, a net monetary benefit and return on investment approach will be applied to estimate the potential value of the new NHF model. The net monetary benefit of an intervention is specified as: $\Delta Cost_{intervention} - \Delta Cost_{consequences}$. Where a net monetary benefit of greater than 0 represents a positive return on investment (where a reduction in cost consequences associated with the intervention is specified as a negative). With respect to return on investment, the direct incremental costs of the intervention ($Cost_{inv}$) are separated from the incremental cost consequences ($Cost_{con}$) associated having made the intervention.

Costs will be measured from activity data with pathway analysis to fully specify all activities in both intervention and control arms. Health service utilisation, adverse reactions, length of stays and associated costs will be obtained from linking the study patient data to QLD health data bases (e.g., T2 costing system). Data on social cost offsets will be collected directly from the patients' carers. Standard discounting will be applied to both cost and outcomes, with uncertainty in the cost and outcome data subjected to sensitivity analyses.

Consumer satisfaction: Data on consumer satisfaction with 12 parents/carers per hospital using a face-to-face structured interview with local clinical staff will be recorded with the GenPrem instrument. The GenPrem is an 8 dimension, 41 item. Patient reported experience measure which explores the domains of Convenience; Communication; Quality; Environment and facilities; Integration; Involvement; Discomfort; and Patient-centred care.

Evaluation of the Implementation outcomes measures:

Implementation Outcomes	Data analysis
Implementation outcomes	Society for the Implementation Research Instrument tool kit.
Use of EBP as a routine treatment locally.	SIRC acceptability measure.
Feasibility of the implemented changes.	SIRC Feasibility measure.
Acceptability of the EBP.	SIRC Adoption measure.
Satisfaction with the use of EBP (all stakeholders).	SIRC Penetration, Adaptability, and Sustainability measures.
Satisfaction with the implementation process.	SIRC Engaging measures (implementation leaders, opinion leaders, champions, external agents).
Evaluation of the EBP implementation is good.	SIRC Executing, Planning, Reflecting and Evaluating Measures.
Recommended for further implementation in other healthcare settings.	SIRC satisfaction and client outcome measures.
Service/Research Outcomes	
Satisfaction with education and competencies associated with AFR management.	SIRC Knowledge and beliefs about the intervention, Individual stage of change, Self-efficacy, Individual stage of change.
Aeroevacuation use is reduced.	Cost analysis of reduced high intensity care.
Electronic medical record prompts are operational.	Audit of electronic records.

Economic evaluation of implementation process

Economic evaluation of implementation strategies for NHF therapy will be examined. Economic evaluations of the implementation will revolve around the costs of different implementation strategies employed in the project and will focus on outcomes relevant to implementation research questions (e.g., acceptability, fidelity, reach) instead of health reported outcomes. Adherence to the respiratory care bundle will be measured by the number of frequency of deviations from the protocol. Specifically, we will consider implementation costs (see **Appendix 4**) to include all processes and strategies required to implement. Depending on how the implementation occurs at each site, implementation cost may vary. The economic evaluation of implementation will be based on a costing study, depending on the differences in implementation strategies used a regression analysis will be conducted to explore the differences between implementation success and depth of strategies used.

Milestones	Deliverables	Performance Indicator	Activity Timeframe
Study Set up Period			
PHASE I Oct 2022 – Sept 2023 (11mths)	Approvals Ethics application Governance application Trial Steering Committee and other relevant investigator meetings/groups established	All legislative requirements met June 2023.	0-9 month
	Personnel recruitment: Project Manager Appointment Educator Appointment	April 2023	0-6 month
	Indigenous Community Officer engagement Staff Interviews for current practice Parent interviews	April 2023	0-6 month
	Clinical consultation Process Local Context Assessment Workshops readiness for Staff Interviews for local Guidelines Approval of local Guidelines Site logistics fact finding visits	August 2023	0-11 month
	Education Material Workshop Development Digital Platform	Griffith Digital Education finalised August 2023	0-11 month
	Database Development	August 2023	0-11 month
	HE Model Development	August 2023	0-11 month
	Randomisation of units (hospitals)	August 2023	10-11month

	Data collection of paediatric ARF admissions in participating sites (historical)	September 2024	0-24 month
Study Implementation Period			
PHASE II Sept 2023 – Mar 2026 31 mths)	Staff Readiness Assessment for Implementation of Respiratory Care Bundle per site	Sept 2023-Mar 2026	At time of site commencement according to randomisation
	Start-up and Ongoing Training Workshops driven by study team	Sept 2023-Mar 2026	At time of site commencement according to randomisation
	Workshops for train the trainer eLearning courses	Sept 2023-Feb 2026	11-39 month according to randomisation of site
	Consultation Feedback (Guideline)	Sept 2023	6-11 month
	Consumer Feedback (Parents)	Sept 2023	6-12 month
	Historical Data collection	Oct 2022-Sept 2025	6-30 month
	Patient screening, data capturing, data cleaning	Sept 2023-Mar 2026	11-40 month
	Measurement of Knowledge Retention (Staff Interviews)	Sept 2023-Mar 2026	11-40 month
	Measurement of Health Economy (Parent interview/questionnaire)	Sept 2023-Mar 2026	11-40 month
	Measurement of Parent Satisfaction (Parent interview/questionnaire)	Sept 2023-Mar 2026	11-40 month
Continuous Education driven locally and by study team	Sept 2023-Mar 2026	11-40 month	
Study Analysis			
PHASE III Mar 2026– Sept 2027 (18 mths)	Observational Data post study collection	Apr 2026-Apr 2027	41-51 month
	Assessment of Sustainability Staff Interviews Consumer Interviews	March 2027	40-52 month
	Reporting/Manuscripts: Main paper HE Paper Implementation Paper Consumer perspective Paper	March 2027	40-60 month
	Conference presentations		52-60 month

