The **socio-economic implications** of a respiratory care bundle that reduces the need for emergency retrieval for rural, remote and especially Indigenous families cannot be understated. The child and parent are removed from a community and flown up to 900kms away into a significantly larger hospital environment, and in the case of Indigenous families the significant cultural differences between staff and families contributes to feelings of powerlessness, fear and isolation [10]. Indigenous communities have repeatedly reported the importance of receiving care on country as it is intrinsically linked with health and wellbeing [11]. Ultimately, it is estimated with a reduction of the high retrieval costs that the savings within this project will surpass the costs of this project alone. The annual transfer rate of 273 (year 2018 and 2019) children in North Queensland per year at an average cost of \$24,500 including back transfer results in \$ 6.1 M expenditure/year and if successful in this project would lead to a yearly cost saving of \$ 2-3 M /year (**Figure 1**).

[figure not shown]

Figure 1

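### As written, the net monetary benefit formula adds the bundle's cost to its savings, so the above-zero rule cannot tell a profitable bundle from a loss-making one

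*Protocol*

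**What the plan says.** Section 8.3 of the protocol sets up an economic evaluation alongside the trial "with primary outcomes of cost benefit/net benefit analysis and cost effectiveness analysis". For the net-benefit part it fixes four things:

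- **Formula.** Net monetary benefit is the change in intervention cost minus the change in cost consequences.
- **Decision rule.** "Where a net monetary benefit of greater than 0 represents a positive return on investment".
- **Sign of savings.** The same sentence adds in parentheses: "where a reduction in cost consequences associated with the intervention is specified as a negative".
- **Sign of spend.** "Incremental cost is the cost difference between the intervention and usual care". The section then describes the incremental costs of the intervention as those incurred in the intervention arm relative to the control arm. Extra spending on the bundle is therefore a positive number.

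The section also keeps the direct cost of the intervention apart from the cost consequences that follow from it, so the two terms of the formula are distinct quantities. The only projected saving is in section 2.1: "if successful in this project would lead to a yearly cost saving of \$ 2-3 M /year". The protocol gives no figure for the cost of the intervention.

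**The concern.** The formula, the sign convention and the decision rule do not fit together. Subtracting a negative number adds it, so savings enter the formula correctly as a gain. The intervention cost, however, also enters with a plus sign and is counted as a gain when it should be a charge. A bundle that spends more then scores higher.

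The defect lies in what the protocol states, not in detail left to a later document: formula, coding and threshold are all given. An analyst who follows them literally would report a positive return for a bundle that loses money. Lower health care costs are part of objectives 1 and 2 (section 3.2) and of the secondary clinical outcomes (section 3.5), and expected savings are a prominent part of the rationale (sections 2.1 and 2.8). A net-benefit result that comes out positive whether or not the bundle pays for itself cannot support that claim.

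**Working it through.** The protocol reports no net monetary benefit, so there is no stated figure to reproduce. The check is algebraic, with numbers only as illustration.

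**Inputs**

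- C = extra spend on the bundle, entered as +C (section 8.3). No value is given, so every C below is an assumption, for the same one-year period as S.
- S = savings in cost consequences, entered as −S (section 8.3). Section 2.1 projects $2-3M per year.

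**Algebra**

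- Formula as written: C − (−S) = C + S.
- True net return: savings minus spend = S − C.
- Difference: (C + S) − (S − C) = 2C. The formula overstates the net return by twice the intervention cost, whatever the savings.
- If cost consequences rise by K instead of falling, the formula gives C − K, which is 0 or below only when K is at least C. The true net is −(C + K), a loss throughout.

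**Numbers ($M; C assumed in every row)**

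| C | Change in cost consequences | As written | Rule says | True net |
|---|---|---|---|---|
| 1 | −2.5 | 1 + 2.5 = +3.5 | positive return | 2.5 − 1 = +1.5 |
| 2.5 | −2.5 | 2.5 + 2.5 = +5.0 | positive return | 2.5 − 2.5 = 0 |
| 5 | −2 | 5 + 2 = +7 | positive return | 2 − 5 = −3 |
| 5 | −3 | 5 + 3 = +8 | positive return | 3 − 5 = −2 |
| 5 | 0 | 5 − 0 = +5 | positive return | 0 − 5 = −5 |
| 3 | +1 | 3 − 1 = +2 | positive return | −1 − 3 = −4 |
| 1 | +3 | 1 − 3 = −2 | not positive | −3 − 1 = −4 |

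The rule gives the same answer in the first six rows, although one is a gain, one breaks even and four are losses. Only the last row, where consequences rise by more than the bundle costs, is called unfavourable.

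**Can another coding rescue the rule?**

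- Savings entered as positive: C − S, which is above 0 exactly when the bundle loses money. This also contradicts the parenthesis on savings.
- A plus sign between the two terms, with savings negative: C + (−S) = C − S, with the same fault.
- Intervention cost entered as a negative outlay: −C − (−S) = S − C, which is correct. It conflicts with the section's description of incremental intervention cost as intervention arm relative to control.

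**The case against.** The best defence is that the sign convention is ambiguous rather than wrong. The sentence defining incremental cost does not spell out the order of subtraction, and if intervention cost were entered as a negative outlay the formula would be right. This does not stand: the same section describes incremental intervention cost as what the intervention arm incurs relative to control, which makes extra spend positive, and nowhere mentions a negative outlay. It does mean that the formula should not be called wrong under every conceivable coding.

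A leading minus sign might also have been lost when the equation was set or converted to text. One such sign on the first term would repair the formula. Nothing in the surrounding text points to it, and the equation otherwise reads as complete.

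The objections on scope do stand. A reader might infer that the whole economic conclusion would be favourable almost whatever the data. The documents do not support that: the ICER is a separate primary economic analysis with its own definition, which the sign error does not touch. Spend and cost consequences are kept apart, and sensitivity analyses are planned, so the components can still be seen. A reader might also take return on investment to be a named primary outcome. Section 8.3 names net benefit and cost effectiveness as primary and treats return on investment as an approach to be applied.

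Nor is there a further fault in expressing the ICER "in the form of the incremental cost per air transport avoided". The same section already plans to set incremental costs against all the primary and secondary endpoints, which covers cost per transfer avoided.

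**Conclusion.** Wrong as written. Under the signs that section 8.3 states, net monetary benefit equals spend plus savings and exceeds the true net return by 2C. With an assumed C of $5M and the projected $2-3M yearly saving, a loss of $3M to $2M would be reported as a benefit of $7M to $8M. With an assumed C of $1M and S of $2.5M, a true gain of $1.5M would be reported as $3.5M. The dollar sizes depend on the assumed C. The sign result does not: it needs only that the bundle costs something.

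It is tempting to say that the rule reverses the truth. It does not: profitable bundles are also called positive, so the fault is that the rule fails to discriminate. The consequence is confined to the net-benefit analysis and to any return on investment computed from it. The trial's clinical conclusions are not at risk, since the ICER, the clinical primary outcome, its model and the sample size do not use this formula.

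**What to change.** In section 8.3, replace the formula with:

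Net monetary benefit = −(change in cost consequences) − (change in intervention cost)

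Keep the convention that a saving is a negative change in cost consequences, and keep the rule that a value above 0 is a positive return. State explicitly that extra spend on the intervention is positive. The quantity is then S − C, which is above 0 only when savings exceed spend.

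Compute return on investment as that quantity divided by the change in intervention cost. In the illustration this gives 1.5 / 1 = 1.5 for C = $1M and S = $2.5M, and −3 / 5 = −0.6 to −2 / 5 = −0.4 for C = $5M and S = $2-3M.

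The cost is one corrected line and one clarifying sentence. No data collection, sample size or clinical procedure changes. Any separate economic analysis plan that repeats the formula should carry the same correction.

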5.2.1 Consent of consumers/parents for the interview

In contrast to data collection on a patient level, we will perform structured interviews with selected consumers/parents and clinicians working in the participating hospitals to obtain information regarding socio-economic factors and their experience during the study.

Potential parent participants will be provided with a participant information sheet either in person or by email or mail. The parent information sheet exists with the Parent Information and Consent Form (PICF) document. Parents will be provided with the information and the interviewer/study coordinator will meet potential participants in person, talk them through the project and invite them to join the project by asking them to formally consent to taking part in an interview. Participation acceptance in the interview is via informed and written consent. Potential participants will be flagged by the clinical staff to the interviewer/study coordinator during the hospital admission of their child. The explanation of the project will be covered in the content of the Parent Information Sheet, for example: what participation involves, confidentiality, and what will happen with the data. Following this explanation and an opportunity for questions to be answered. Written informed consent will be obtained and participants will be asked if a suitable time could be arranged to participate in a face-to-face

interview or telephone/video interview that may take up to one hour. Potential participants will be provided with contact details for the study coordinator if they wish to take time to consider participation.

All participants will be informed of their right to not participate or to withdraw from the project without prejudice, and to withdraw unprocessed data. Participants will be invited to provide a mailing or email address if they would like their interview transcript returned to them so they can review, approve or correct it prior to processing, and/or if they would like to have copies of the project results sent directly to them upon conclusion, analysis and write up of the project.

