We acknowledge that the interview process may cause some distress to parents/carers. Potential participants will be flagged by the clinical staff with the understanding of the current emotional and social situation of the participant. For indigenous participants we anticipate to have an Indigenous interviewer. We will also use the Indigenous Liaison Officer in each hospital. The interviewer will inform participants that if the interview causes them distress to please let the interviewer know. The interview can be stopped at any time and they can be referred to a counsellor or someone else to talk to. If they become distressed after the interview, contact details for available services are listed on their information sheet.

The parent information sheet (information section of the PICF) will be distributed to parents of children with ARF to inform them that some parents may be interviewed, and questions asked in relation to their experience in hospital. The parent information sheet explains the aim of this interview to capture quality of life information from the parent/guardians (for the child by proxy) and to determine the burden and impact which takes place when their child is admitted to hospital. The interview may occur whilst the child is in hospital or after discharge home (within 4 weeks preferentially).

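### Section 8.3 has parents complete the GenPrem with local clinical staff, which conflicts with the separate interviewer in 5.2.1 and risks bias in the satisfaction outcome

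*Protocol*

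**What the plan says.** The protocol describes the parent interview in several places.

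- **8.3, Consumer satisfaction.** Data come from 12 parents or carers per hospital, "using a face-to-face structured interview with local clinical staff will be recorded with the GenPrem instrument". The instrument has 41 items in eight dimensions, among them communication, quality, involvement and patient-centred care.
- **5.2.1, Consent for the interview.** Clinical staff have one task: "Potential participants will be flagged by the clinical staff to the interviewer/study coordinator during the hospital admission of their child". After that, "the interviewer/study coordinator will meet potential participants in person, talk them through the project and invite them to join the project". The same section has the interviewer tell parents what to do if the interview distresses them, and adds: "For indigenous participants we anticipate to have an Indigenous interviewer". The appointment is for a face-to-face "interview or telephone/video interview that may take up to one hour".
- **7.1, Data Collection.** "Use of the GenPrem instrument will be for the parent as proxy for the child and as the parent for their own experience" with the child's admission. The respondent is therefore the parent.
- **7.2, Parent interviews.** "A structured interview with 12 parents per hospital in the Control Phase and 12 parents in the Implementation phase". Section 5.2 gives the same numbers. Section 7.2 does not say who conducts the interview.
- **3.5 and 3.6.** Consumer satisfaction is secondary clinical outcome 6, covering both staff and parents or carers. Patient/carer satisfaction is health service outcome 5.

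**The concern.** The protocol gives two answers to the question of who sits across from the parent. A site that follows 5.2.1 uses someone outside the treating team, in person or remotely. A site that follows 8.3 uses its own clinical staff, in person only. Satisfaction data from the 14 hospitals could then be collected in different ways.

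The 8.3 arrangement is also the weaker one. Parents asked by the hospital's own staff how well that staff communicated and cared for their child have a reason to answer kindly. The GenPrem asks about exactly these matters.

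The outcome is put to use. Section 8.3 sets incremental costs against every primary and secondary endpoint in natural units, which calls for an intervention-minus-control difference in satisfaction. The milestones also list a paper on the consumer perspective.

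**Working it through.** No sample size, error rate or event count is involved, and the protocol gives no figure to reproduce. The check is a comparison of text followed by a short argument about bias.

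**Step 1. Compare the sections.**

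| Item | 5.2.1 | 8.3 |
|---|---|---|
| Task of clinical staff | Flag candidates | Take part in the interview |
| Who meets the parent | Interviewer/study coordinator; Indigenous interviewer anticipated for Indigenous families | Local clinical staff (plain reading) |
| Mode | Face-to-face, telephone or video | Face-to-face only |

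The rows on staff and mode cannot both be followed as written.

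**Step 2. Test the other reading of 8.3.** Section 7.2 uses almost the same phrase about local clinical staff where staff are the people being interviewed, and 3.5 includes staff in the satisfaction survey. The sentence in 8.3 could therefore have lost an *and*, with parents and staff both meant as respondents. But 7.1 makes the parent the GenPrem respondent, and 8.3 itself calls it a patient-reported experience measure. On that reading, staff would be placed on an instrument not meant for them. The sentence needs correction either way.

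**Step 3. Ask when the phase contrast is biased.** Let S_C and S_I be the true mean satisfaction in the control and intervention phases, and b_C and b_I the inflation caused by answering to hospital staff. The observed contrast is

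(S_I + b_I) − (S_C + b_C) = (S_I − S_C) + (b_I − b_C).

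- If b_I = b_C, the inflation cancels in the contrast, although the satisfaction level in each phase is still too high.
- If b_I differs from b_C, the difference passes straight into the estimated effect.

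**Step 4. Ask whether a difference is plausible.** Staff know which phase their hospital is in. They are trained in the bundle during the transition month (4.1, 6.2.2), and each hospital names a doctor and a nurse or allied health champion (4.2.2). A change in how staff put the questions, or in how parents answer them, is possible. Nothing in the protocol measures it, so b_I − b_C has no derivable value.

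**The case against.** The strongest reply is that this is loose drafting. Section 5.2.1 is the detailed account of the interview, sites would presumably follow it, and the phrase in 8.3 may simply mean that staff are surveyed as well. The ambiguity is real, and for that reason the fix should not delete a staff survey that may be intended. It does not clear the sentence, as step 2 shows.

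A second reply is that bias common to both phases cancels. That is correct, and it limits the point to a risk.

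Three stronger readings are tempting, and the documents do not support them.

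- A reader might infer that 8.3 leaves only 12 interviews per hospital in total, too few for a phase comparison. Section 8.3 never says in total, and 5.2 and 7.2 both set 12 per hospital in each phase.
- A reader might infer that 7.2 also contradicts 8.3 on the interviewer. Section 7.2 names none, so the conflict is with 5.2.1 alone.
- A reader might want to show that courtesy bias could by itself produce a significant difference. That needs an assumed satisfied/not satisfied endpoint and an assumed size of artefact. The protocol defines no such endpoint for the GenPrem and supplies neither figure.

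**Conclusion.** The inconsistency stands. On its plain reading, 8.3 contradicts 5.2.1 on who interviews the parent and on the permitted modes, and it chooses an arrangement prone to socially desirable answers in secondary outcome 6. Bias in the phase contrast is plausible but not established, and its size cannot be stated. This conclusion rests on reading 8.3 as naming the interviewer. If it names extra respondents, the fault is the use of a parent-reported instrument for staff. The primary outcome does not depend on these interviews, because transfers are taken from medical records. This is a minor correction, worth making because it is cheap.

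**What to change.** In 8.3, under Consumer satisfaction:

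1. State that the GenPrem is administered to parents or carers by the interviewer/study coordinator described in 5.2.1, and not by staff who treated the child.
2. Allow the same modes as 5.2.1: face-to-face, telephone or video.
3. Refer to 5.2 and 7.2 for the number of interviews in each phase.
4. Describe any staff satisfaction survey in its own sentence, with its own instrument, so that the staff part of secondary outcome 6 is kept.

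The milestones run parent-satisfaction measurement from September 2023 to March 2026, so some interviews may already have been done. Recording the interviewer's role and the mode for each one would let any difference be examined.

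The cost is a few sentences. The role is already planned, so no new staff are needed; some interviews may move to telephone or video. The edit does not remove knowledge of the phase, since 6.2.2 has the study coordinator help train the research nurses. It does remove the need for parents to rate care in front of those who gave it.
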